6.1 Inclusion Criteria

Each patient must meet the following criteria to be enrolled in this study:

1. The patient is ≥ 18 years of age.
2. The patient who has received an adequate information and provided informed consent for all the study-specific procedures in advance
3. The patient has histologically or cytologically confirmed gastric carcinoma, including gastric adenocarcinoma or GEJ adenocarcinoma. (Patients with adenocarcinoma of the distal esophagus are eligible if the primary tumor involves the GEJ.) patient has metastatic disease or locally recurrent,

[Type here]

[Type here]

[Type here]

Pembrolizumab + Ramucirumab (Ver 2.5, Oct 2024)

unresectable disease.

4. The patient's tumor tissue must have the pre-defined characteristics as follows ;
EBV+ or PDL1 CPS \geq 5
5. The patient has measureable or evaluable disease as determined by standard computed tomography (CT) or magnetic resonance imaging (MRI) imaging. Examples of evaluable, nonmeasurable disease include gastric, peritoneal, or mesenteric thickening in areas of known disease, or peritoneal nodules that are too small to be considered measurable by Response Evaluation Criteria in Solid Tumors (RECIST version 1.1)
6. The patient has experienced disease progression during first-line treatment or second-line therapy for metastatic disease.
 - Acceptable prior chemotherapy regimens for this protocol are combination chemotherapy regimens that include platinum and/or fluoropyrimidine components (acceptable prior platinum agents are cisplatin, carboplatin, or oxaliplatin; acceptable prior fluoropyrimidine agents are 5-FU, capecitabine, or S-1). Regimens including a third agent, such as an anthracycline or a taxane, are acceptable provided a fluoropyrimidine and/or a platinum were used.
 - Recurrence during or within 6 months of completion of adjuvant chemotherapy (capecitabine, 5-FU, or TS-1) will be considered as first-line chemotherapy.
7. No prior exposure to anti-PD1 antibody or ramucirumab. Or ramucirumab can participate if the investigator determines that there is a clinical benefit.
8. The patient has an Eastern Cooperative Oncology Group performance status (ECOG PS) score of 0 or 1.
9. Patients must have acceptable bone marrow, liver and renal function measured within 28 days prior to administration of study treatment as defined below:
 - ✓ Haemoglobin \geq 9.0 g/dL
 - ✓ Absolute neutrophil count (ANC) $\geq 1.5 \times 10^9$ /L
 - ✓ Platelet count $\geq 100 \times 10^9$ /L

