 - ✓ Total bilirubin $\leq 1.5 \times$ institutional upper limit of normal (ULN)
 - ✓ AST (SGOT)/ALT (SGPT) $\leq 3.0 \times$ institutional upper limit of normal unless liver metastases are present in which case it must be $\leq 5 \times$ ULN
 - ✓ Serum creatinine $\leq 1.5 \times$ institutional ULN
 - ✓ Glomerular filtration rate < 45 mL/min in assessed by standard methods in the laboratory
 - ✓ urinary protein is $\leq 1+$ on dipstick or routine urinalysis
 - ✓ (INR) ≤ 1.5 and (PTT) \leq x5 seconds above the ULN (unless receiving anticoagulation therapy). Patients on anticoagulation therapy with unresected primary tumors or local tumor recurrence following resection are not eligible.

[Type here]

[Type here]

[Type here]

11. Female patients of childbearing potential must have a negative pregnancy test (urine or serum), must not be breastfeeding and using adequate contraceptive measures.

Female patients must use a highly effective contraceptive measure from screening until 4 months after the last dose of drug. All methods of contraception (except for total abstinence) should be used in combination with the use of a condom by a male sexual partner for intercourse (see Restrictions below). (or vasectomy)

Female patients must have evidence of non-childbearing potential by fulfilling one of the following criteria at screening:

- a. Post-menopausal women defined as aged more than 50 years and amenorrhoeic for at least 12 months following cessation of all exogenous hormonal treatment.
- b. Documentation of irreversible surgical sterilisation by hysterectomy, bilateral oophorectomy, or bilateral salpingectomy, but not tubal ligation.

11-1. For the duration of the study and for 1 week after the last study drug administration, sexually active male patients must be willing to use barrier contraception i.e. condoms with all sexual partners. Where the sexual partner is a 'women of child-bearing potential' who is not using effective contraception, men must use a condom (with spermicide) during the study and for 6 months after the last dose of a study drug. (or vasectomy)

12. Biopsy during the screening window prior to dosing and at before cycle 3 (if clinically feasible)

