13. The patient has received prior therapy with an agent that directly inhibits VEGF (including bevacizumab), or VEGF Receptor 2 activity, or any antiangiogenic agent and immunotherapy.
14. The patient is receiving chronic antiplatelet therapy, including aspirin, nonsteroidal anti-inflammatory drugs (NSAIDs; including ibuprofen, naproxen, and others), dipyridamole or clopidogrel, or similar agents. Once-daily aspirin use (maximum dose 325 mg/day) is permitted.
15. The patient has a known allergy to any of the treatment components.
16. Has had a prior anti-cancer monoclonal antibody (mAb) within 4 weeks prior to study Day 1 or who has not recovered (i.e., \leq Grade 1 or at baseline) from adverse events due to agents administered more than 4 weeks earlier.
17. Has active autoimmune disease that has required systemic treatment in the past 2 years (i.e. with use of disease modifying agents, corticosteroids or immunosuppressive drugs). Replacement therapy (eg., thyroxine, insulin, or physiologic corticosteroid replacement therapy for adrenal or pituitary insufficiency, etc.) is not considered a form of systemic treatment.
18. Has a history of (non-infectious) pneumonitis that required steroids or has current pneumonitis.
19. Has an active infection requiring systemic therapy.
20. Has a known history of Human Immunodeficiency Virus (HIV) (HIV 1/2 antibodies).
21. Has known active Hepatitis B or Hepatitis C (e.g., HCV RNA [qualitative] is detected) and liver cirrhosis. Chronic HBV infection with anti-viral agent prophylaxis is allowed.
22. Has known liver cirrhosis at a level of Child-Pugh B (or worse) or cirrhosis (any degree) and a history of hepatic encephalopathy or clinically meaningful ascites resulting from cirrhosis. Clinically meaningful ascites is defined as ascites from cirrhosis requiring diuretics or paracentesis.
23. The patient is pregnant or breastfeeding.

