Appendix 2 (Cyramza Safety Language)

The following items MUST be included in the appropriate Inclusion/Exclusion Criteria/Discontinuation sections as well as in the text of the appropriate or corresponding section of the protocol:

Hematologic Function

To be included in a ramucirumab clinical trial:

The patient has adequate hematologic function, as evidenced by an absolute neutrophil count (ANC) $\geq 1500/\mu\text{L}$, hemoglobin ≥ 9 g/dL (5.58 mmol/L), and platelets $\geq 100,000/\mu\text{L}$.

Coagulation:

The patient has adequate coagulation function as defined by International Normalized Ratio (INR) ≤ 1.5 and a partial thromboplastin time (PTT) (PTT/aPTT) $< 1.5 \times$ upper limits of normal [ULN]. Patients on full-dose anticoagulation must be on a stable dose (minimum duration 14 days) of oral anticoagulant or low molecular weight heparin (LMWH). If receiving warfarin, the patient must have an INR ≤ 3.0 . For heparin and LMWH there should be no active bleeding (that is, no bleeding within 14 days prior to first dose of protocol therapy) or pathological condition present that carries a high risk of bleeding (for example, tumor involving major vessels or known varices).

For Ramucirumab combined with Chemotherapy studies:

Coagulation: The patient must have adequate coagulation function as defined by International Normalized Ratio (INR) ≤ 1.5 , and a partial thromboplastin time (PTT) ≤ 5 seconds above the ULN (unless receiving anticoagulation therapy). Patients receiving warfarin must be switched to low molecular weight heparin and have achieved stable coagulation profile prior to first dose of protocol therapy.

To be excluded from a ramucirumab clinical trial:

The patient has experienced any Grade 3-4 GI bleeding within 3 months prior to first dose of protocol therapy.

The patient has a history of deep vein thrombosis (DVT), pulmonary embolism (PE), or any other significant thromboembolism (venous port or catheter thrombosis or superficial venous thrombosis are not considered “significant”) during the 3 months prior to first dose of protocol therapy.

Discontinuation of patient from a ramucirumab clinical trial:

Patients with unresected primary tumors (or local recurrence) who develop Grade 3 and 4 venous thromboembolism may also receive anticoagulation and continue ramucirumab therapy provided that the tumor does not confer an excessive bleeding risk, in the opinion of the patient’s physician.

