Grade 3 and 4 arterial thromboembolic events, or any PE/DVT occurring or worsening during anticoagulant therapy, require permanent discontinuation of ramucirumab therapy. Any venous or arterial event leading to discontinuation of ramucirumab therapy will be considered serious and should be reported via the serious adverse event (SAE) mechanism.

Hepatic Function

To be included in a ramucirumab clinical trial:

[Type here]

[Type here]

[Type here]

The patient has adequate hepatic function as defined by a total bilirubin ≤ 1.5 times the upper limit normal (ULN), and aspartate transaminase (AST) and alanine transaminase (ALT) ≤ 3.0 times the ULN or 5.0 times the ULN in the setting of liver metastases.

To be excluded from a ramucirumab clinical trial:

The patient has:

- cirrhosis at a level of Child-Pugh B (or worse) or
- cirrhosis (any degree) and a history of hepatic encephalopathy or clinically meaningful ascites resulting from cirrhosis. Clinically meaningful ascites is defined as ascites from cirrhosis requiring diuretics or paracentesis.

Discontinuation of a patient from a ramucirumab clinical trial:

Any patient who experiences signs of hepatic encephalopathy or other serious signs of liver impairment such as hepatorenal syndrome must be permanently discontinued from ramucirumab therapy.

Renal Function

To be included in a ramucirumab clinical trial:

The patient has adequate renal function as defined by a serum creatinine ≤ 1.5 times the ULN, or creatinine clearance (measured via 24-hour urine collection) ≥ 40 mL/minute (that is, if serum creatinine is > 1.5 times the ULN, a 24-hour urine collection to calculate creatinine clearance must be performed). (unless IIT designed to study ramucirumab administration in patients with renal impairment).

The patient's urinary protein is $\leq 1+$ on dipstick or routine urinalysis (UA; if urine dipstick or routine analysis is $\geq 2+$, a 24-hour urine collection for protein must demonstrate < 1000 mg of protein in 24 hours to allow participation in this protocol).

Discontinuation of a patient from a ramucirumab clinical trial:

The patient will have ramucirumab permanently discontinued if the protein level is > 3 g/24 hours, if there is a third occurrence of > 2 g/24 hours, or if the protein level does not return to < 2 g/24 hours within 2 weeks.

Cardiac Function

To be excluded in a ramucirumab clinical trial:

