The patient has experienced any arterial thromboembolic events, including but not limited to myocardial infarction, transient ischemic attack, cerebrovascular accident, or unstable angina, within 6 months prior to first dose of protocol therapy.

The patient has uncontrolled or poorly-controlled hypertension (> 160 mmHg systolic or > 100 mmHg diastolic for > 4 weeks) despite standard medical management.

Discontinuation of a patient from a ramucirumab clinical trial:

Patients with grade 4 hypertension must not receive further treatment with Ramucirumab.

Reproductive Precautions

To be included in a ramucirumab clinical trial:

[Type here]

[Type here]

[Type here]

Pembrolizumab + Ramucirumab (Ver 2.5, Oct 2024)

Because the teratogenicity of ramucirumab is not known, the patient, if sexually active, must be postmenopausal, surgically sterile, or using effective contraception (hormonal or barrier methods). Female patients of childbearing potential must have a negative serum pregnancy test within 7 days prior to first dose of protocol therapy.

To be excluded from a ramucirumab clinical trial:

The patient is pregnant or breast-feeding.

The patients with lung cancer (NSCLC and SCLC) regardless of tumor histology should be excluded from a ramucirumab clinical trial:

If they experience hemoptysis (defined as bright red blood or $\geq 1/2$ teaspoon) within 2 months prior to first dose of protocol therapy or with radiographic evidence of intratumor cavitation or has radiologically documented evidence of major blood vessel invasion or encasement by cancer.

General Medical Disorders

Discontinuation of a patient from a ramucirumab clinical trial:

Patients with grade 3 or 4 infusion-related reactions must not receive further treatment with ramucirumab.

Ramucirumab should be permanently discontinued in the event of a gastrointestinal perforation or fistula formation.

If Reversible Posterior Leukoencephalopathy (RPLS) is diagnosed, ramucirumab must be permanently discontinued. All cases of RPLS must be reported via the SAE mechanism.

Prior Medical History Precautions

To be excluded from a ramucirumab clinical trial:

The patient has a prior history of GI perforation/fistula (within 6 months of first dose of protocol therapy) or risk factors for perforation.

The patient has a serious or nonhealing wound, ulcer, or bone fracture within 28 days prior to first dose of protocol therapy.

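### Eligibility rules are wrong or contradictory as written: acceptable renal function is defined by GFR below 45 mL/min, and Section 6.1 item 7 allows prior ramucirumab that the synopsis, Section 6 and exclusion 13 bar

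*Combined protocol and SAP*

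**What the plan says.** **Renal function.** Section 6.1 item 9 opens with a requirement: "Patients must have acceptable bone marrow, liver and renal function measured within 28 days prior to administration of study treatment as defined below". One line of the list beneath it is "Glomerular filtration rate < 45 mL/min in assessed by standard methods in the laboratory". The synopsis has the same line. A separate line caps serum creatinine at 1.5 times the ULN. Appendix 2 (Renal Function) is built differently: creatinine up to 1.5 times the ULN, or "creatinine clearance (measured via 24-hour urine collection) ≥ 40 mL/minute", the clearance being needed when creatinine is above that limit.

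**Prior ramucirumab.** Synopsis item 7 bars prior anti-PD1 antibody or ramucirumab without exception. Section 6.1 item 7 repeats the bar and adds "Or ramucirumab can participate if the investigator determines that there is a clinical benefit". Exclusion 13, in the synopsis and Section 6.2, covers this case: "The patient has received prior therapy with an agent that directly inhibits VEGF (including bevacizumab), or VEGF Receptor 2 activity". The opening paragraph of Section 6 also excepts earlier anti-angiogenic treatment from the prior regimens it accepts.

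**GI perforation or fistula.** Appendix 2 begins "The following items MUST be included in the appropriate Inclusion/Exclusion Criteria/Discontinuation sections" and, under Prior Medical History Precautions, excludes a patient when "The patient has a prior history of GI perforation/fistula" applies within 6 months of the first dose, or when there are risk factors for perforation. No item in Section 6.2 or the synopsis exclusions carries this.

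**The concern.** Section 6.3 says that the enrolment criteria are to be followed explicitly, so staff are not free to guess the intended sense of a line. Under the GFR line as written, a patient with GFR of 45 or above is either refused or enrolled against the text. Either way, the eligibility record and the protocol cannot both be right.

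The ramucirumab conflict bears on the primary endpoint. This is a single-arm, open-label trial, and Section 13.1.1 divides responders by every patient given any study treatment. Nothing in Section 13 separates patients already exposed to one of the two study drugs. If item 7 were used on its own, an investigator's judgement of likely benefit would decide whether such patients enter that denominator, and the ORR would describe a population other than the one in Section 6 and the synopsis.

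**Working it through.** The plan states no figure on this point, so the check sets the rules side by side.

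**1. The GFR line as written.**
- Item 9 is a list of things a patient must have, not a list of exclusions. GFR < 45 therefore accepts values below 45 and rejects values of 45 and above.
- The line has no lower limit. The only other limit on renal impairment in item 9 is serum creatinine ≤ 1.5 × ULN, which must also be met.
- A text-reading error is unlikely. The sign is the same in the synopsis and Section 6.1, and the neighbouring ≥ and ≤ signs came through intact.

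**2. The GFR line against Appendix 2.**
- Creatinine ≤ 1.5 × ULN: Appendix 2 is satisfied whatever the clearance. Item 9 is satisfied only if GFR is also below 45. A patient with normal creatinine and GFR of, say, 90 passes Appendix 2 and fails item 9.
- Creatinine > 1.5 × ULN: Appendix 2 is satisfied if clearance is ≥ 40 mL/min. Item 9 fails on creatinine.
- Direction: if GFR and creatinine clearance are put on one scale (an assumption), < 45 and ≥ 40 share only the band from 40 to below 45. In whole numbers from 0 to 150, that is 40 to 44. Of the rest, 40 values (0 to 39) meet only the item 9 line and 106 values (45 to 150) meet only the Appendix 2 floor.
- The passages thus differ in direction and also in form. The Appendix 2 floor is an alternative for raised creatinine, not a GFR floor for every patient.

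**3. Prior ramucirumab.**
- Section 4.4 describes ramucirumab as an antibody that blocks the binding of VEGF to VEGF Receptor 2, so prior ramucirumab meets exclusion 13. The closing words of exclusion 13, which join antiangiogenic agents and immunotherapy, are ambiguous, but the VEGF Receptor 2 limb is enough.
- Section 6.2 bars a patient who meets any one exclusion. Everyone who could use the item 7 exception meets exclusion 13. Applied together, the rules admit none of them.
- Applied alone, item 7 admits them at the investigator's discretion.
- The exception appears only in Section 6.1, so the synopsis and the body also disagree on item 7.

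**4. Reach.**
- Every screened patient meets item 9. Section 12 gives a maximum of 26 patients (Section 7.1 says 35).
- With 25 patients in the denominator, one response is 1/25 = 4 percentage points of ORR. Even a few pretreated patients could move the estimate visibly, in a direction the documents do not let us predict.

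**5. Perforation or fistula.** The items of Section 6.2 and the synopsis exclusions were read against Appendix 2. The closest entries concern GI bleeding and nonhealing wounds or ulcers. None mentions perforation or fistula.

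**The case against.** The case for leaving the text alone is that these are drafting slips. Staff would notice the GFR sign, the creatinine limit still applies, and exclusion 13 already stops anyone whom item 7 might let in. Appendix 2 is also visibly generic text: it contains lung-cancer exclusions and wording for chemotherapy combinations, so not every line was written with this trial in mind. Much of this stands. It lowers the likely harm, and it makes the perforation gap the lesser point. It does not make the rules consistent, and Section 6.3 leaves no room for silent correction.

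Four stronger readings are tempting, and the documents do not support them.
- *The trial selects patients with failing kidneys.* The creatinine limit must also be met, and nothing shows how the GFR line was applied in practice.
- *Pretreated patients are in the ORR.* That requires exclusion 13 to be set aside, and the documents do not show that it was.
- *The trial loses power.* The design inputs (15% against 40%, 25 evaluable patients) do not depend on these criteria. The documents give neither the number of pretreated patients nor their response rate. Under the plan's own rule of 7 or more responses in 25, two-stage exact power is 92.6% at 40%. Assume that 5 of 25 are pretreated. If they respond at 15%, the average rate is (20 × 0.40 + 5 × 0.15)/25 = 35%, and power at 35% is 82.5%. If they respond at 40%, nothing is lost. This range only reflects the assumptions, so it cannot serve as the size of the problem.
- *The primary ORR should be restricted to patients without prior ramucirumab.* Section 13.1.1 defines an all-treated set. Removing treated patients would depart from it and leave fewer than the 25 on which the decision rule was built.

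**Conclusion.** The eligibility text is wrong as written on two counts. The GFR line contradicts its own heading in effect, and it differs from Appendix 2 in direction and form. Section 6.1 item 7 contradicts synopsis item 7, Section 6 and exclusion 13. The missing perforation/fistula exclusion is a true but lesser omission.

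The first fault touches every patient screened. The second changes whom the ORR describes only if item 7 was used without exclusion 13; how often that happened, if at all, cannot be known from the documents. The conclusion rests on the wording alone. The one assumption, a common scale for GFR and clearance, serves only to show that the limits run in opposite directions. No numerical loss of power or bias is claimed, and no view is taken on which renal limit or which rule on prior ramucirumab is right.

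**What to change.** 1. Reconcile the GFR criterion in the synopsis and Section 6.1 with the item 9 heading and with the Renal Function text of Appendix 2, in direction, limit and form. The sponsor decides the content.
2. Reconcile Section 6.1 item 7 with synopsis item 7, the opening of Section 6 and exclusion 13, so that one consistent rule on prior ramucirumab remains.
3. Reconcile Section 6.2 and the synopsis with the Appendix 2 perforation/fistula item, either by including it or by stating why it does not apply to this trial.
4. Check the eligibility records of enrolled patients against the reconciled text, and list any who do not meet it.
5. In Section 13.1.1, keep the all-treated set as the primary ORR population. If any ramucirumab-pretreated patient was treated, add a sensitivity ORR without those patients, with its exact 95% interval, and report how many were left out.

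The cost is amendment wording, a record check for at most 26 patients (35 if Section 7.1 is the figure in force), and at most one extra line in the efficacy table. The sample size and the stopping and decision rules are not affected.
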